2.2 Hypotheses and/or Estimations

Null Hypothesis

The treatment effect of apremilast 30 mg BID and placebo is equivalent.

Alternative Hypothesis

There is a difference in treatment effect between apremilast 30 mg BID and placebo.

3. Study Overview

3.1 Study Design

This is a phase 3, multicenter, randomized, double-blind, placebo-controlled study evaluating the efficacy and safety of apremilast 30 mg BID versus placebo in Japanese subjects with PPP.

Approximately 170 subjects will be randomized in a 1:1 ratio to 1 of 2 treatment groups: apremilast 30 mg BID or placebo. Subject randomization will be stratified by a subject's rounded PPPASI total score ($\leq 20/21-30/ \geq 31$) and focal infection status (yes/no) at baseline.

Randomized subjects will receive either apremilast 30 mg BID or placebo for 16 weeks, the duration of the double-blind placebo-controlled treatment period. During the active treatment period (week 16 to week 52), all subjects will receive apremilast 30 mg BID. After the final dose treatment, subjects will enter a 30-day safety observational follow-up period. The total study duration including 4 weeks screening per subject is approximately 60 weeks.

The primary analysis will be performed after all subjects have either completed the week 16 visit (visit 8) or have discontinued the study. A supplemental analysis will be conducted after all subjects have either completed the week 24 visit (visit 10) or have discontinued the study. The final analysis will be conducted after all subjects have either completed the week 56 visit (visit 14) or discontinued the study.

3.2 Sample Size

The primary endpoint is the achievement of PPPASI-50 response at week 16. The sample size estimation is based on the results of the phase 2 study (CC-10004-PPP-001 [20200055]). Assuming a proportion of subjects achieving PPPASI-50 response at week 16 of 40% and 65% for the placebo group and the apremilast 30mg BID group, respectively, a sample size of approximately 170 subjects in total (85 subjects per group) provides 90% power using a chi-square test with a 2-sided alpha of 0.05. A dropout rate of 5% during double-blind placebo-controlled treatment period is anticipated.

4. Covariates and Subgroups

4.1 Planned Covariates

For the secondary endpoints to be analyzed with MMRM model (i.e., change from baseline at week 16 in PPPASI total score, PPSI total score, subject's VAS for PPP

symptoms [pruritus and pain/discomfort], DLQI total score), the corresponding baseline value of the endpoint will be included as a covariate in the model.

4.2 Subgroups

The primary endpoint (PPPASI-50 response at week 16) and the selected key secondary endpoints such as change from baseline at week 16 in PPPASI total score and PPSI total score will be examined in the following subgroups to investigate the consistency of treatment effects. For each subgroup, a category with an insufficient number of subjects may be pooled.

- Age (< 40, ≥ 40 to < 65, ≥ 65 years)
- Sex (male, female)
- BMI category (< 25, ≥ 25 to < 30, ≥ 30 kg/m²)
- Tobacco Use (current/former, never)
- Duration of PPP (< 2, \geq 2 to < 6, \geq 6 to < 10, \geq 10 years)
- PPPASI total score range at baseline (clinical data) ($\leq 20, \geq 21$ to $\leq 30, \geq 31$)
- Presence of focal infection at baseline (clinical data) (Yes, No)
- Presence of pustulotic arthro-osteitis (PAO) at baseline (Yes, No)
- Presence of nail lesion at baseline (Yes, No)
- Prior use of biologic disease modifying anti-rheumatic drugs (DMARDs) for PPP (Yes, No)
- History of focal infection including periodontitis, tonsilitis and sinusitis (Yes, No)
- •

5. Definitions

5.1 Safety Related Definitions

5.1.1 Treatment-emergent Adverse Events (TEAEs)

Any AEs that begin or worsen on or after the first dose of IP through 30 days after the last dose of IP or study treatment discontinuation date, whichever is later.

5.1.2 Treatment-related Adverse Events (TRAEs)

A treatment-related AE is any treatment-emergent AE with the relationship flag on the Events eCRF indicating there is a reasonable possibility that the event may have been

caused by investigational medicinal product. In the unlikely event that the relationship is missing, the treatment-emergent event will be considered treatment-related and documented in a footnote of the treatment-related summary.

5.2 Study Dates/Timelines

5.2.1 Enrollment Date

Enrollment date is defined as the randomization date.

5.2.2 End of IP Admin Date

End of IP Admin for each subject is defined as the date the decision was made to end IP as recorded on the End of IP CRF page.

5.2.3 Last IP Dose Date

Last IP Dose Date for each subject is defined as the latest date IP is administered.

5.2.4 Randomization Date

Randomization date is defined as the date subject was allocated to a treatment group.

5.2.5 Study Day

The number of days from Study Day 1, inclusive, given by the following formula:

- Study Day = (Date of interest Date of Study Day 1) + 1, if date of interest is on/after Study Day 1.
- Study Day = (Date of interest Date of Study Day 1), if date of interest is before Study Day 1.

Study Day 1 is defined as the first day of IP administration after randomization. If a subject is randomized but never dosed, then set Study Day 1 to randomization date.

5.2.6 Study End Date

The Study End Date is defined as the last End of Study (EOS) date of all enrolled subjects.

5.2.7 Subject-level End of Study (EOS) Date

End of study for each subject is defined as the date the subject last completed a protocol-specified measurement.

5.2.8 Treatment duration

Last IP Dose Date minus Study Day 1 plus 1.

5.3 Baseline Related Definitions

5.3.1 Change from baseline

The arithmetic difference between a post-baseline value and baseline for a given time point: Change from baseline = (post-baseline value – baseline value).

5.3.2 Percent Change from Baseline

The percent change from baseline for a given variable at a given time point is defined as: 100 x [(value at given time point – baseline value) / baseline value]. Subjects with a zero value at baseline will be excluded from the summary of percent change from baseline.

5.4 Study Endpoints

5.4.1 Palmoplantar Pustulosis Area and Severity Index (PPPASI)

PPPASI is a disease-specific efficacy assessment tool used by investigators established to detect a change of disease status on palms or soles. In the PPPASI system, the palms and soles are divided into 4 regions: the right palm, left palm, right sole, and left sole, which account for 20%, 20%, 30%, and 30% of the total body surface area (BSA) of the palms and soles, respectively. The scoring system for the signs of the disease (E = erythema, P = pustules/vesicle and D = desquamation/scale) is: 0 = none, 1 = slight, 2 = moderate, 3 = severe, and 4 = very severe. The scale for estimating the area of involvement for pustular lesions is: 0 = no involvement, 1 = 1% to 9% involvement, 2 = 10% to 29% involvement, 3 = 30% to 49% involvement, 4 = 50% to 69% involvement, 5 = 70% to 89% involvement, and 6 = 90% to 100% involvement.

The PPPASI total score formula is as below.

CONFIDENTIAL

PPPASI total score = (E + P + D)×Area×0.2 [right palm] + (E + P + D)×Area×0.2 [left palm] + (E + P + D)×Area×0.3 [right sole] + (E + P + D)×Area×0.3 [left sole]

PPPASI produces numeric total scores that can range from 0 to 72. A higher score indicates more severe disease.

The PPPASI sub-score is defined as the PPPASI total score including only one subdomain of interest. For example, the PPPASI sub-score for erythema will be calculated as below.

PPPASI sub-score (Erythema) = (E)×Area×0.2 [right palm] + (E)×Area×0.2 [left palm] + (E)×Area×0.3 [right sole] + (E)×Area×0.3 [left sole]

PPPASI-50, PPPASI-75, and PPPASI-90 are defined as \geq 50%, \geq 75%, and \geq 90% improvement (reduction) in PPPASI total score from baseline, respectively.

5.4.2 Palmoplantar Pustulosis Severity Index (PPSI)

PPSI is a disease-specific efficacy assessment tools by investigators. This is established to detect a change of disease status on a specified palm or sole. Evaluated skin lesion is identified by either right or left palm or sole, which has the most severe skin lesion at baseline and the identified skin lesion site will be assessed at all subsequent visits. Evaluation of skin lesion site are assessed separately for erythema (E), pustules/vesicle (P) and desquamation/scale (D), which are each rated on a scale of 0 to 4: 0 = none, 1 = slight, 2 = moderate, 3 = severe, and 4 = very severe.

The severity of the disease is calculated with the PPSI total score formula as below.

• PPSI total score= (E + P + D)

PPSI sub-score (Erythema) = E.

The total score ranges from 0 to 12. A higher score indicates more severe disease.

PPSI-50 and PPSI-75 are defined as \geq 50% and \geq 75% improvement (reduction) in PPSI total score from baseline, respectively.

5.4.4 Pruritis and Pain Assessment with Subject Visual Analogue Scale (VAS) for PPP Symptoms

Subjects will use VAS (with scores ranging from 0 to 100, with 100 being most severe) to assess the degree of PPP pain/discomfort and pruritus on the hands and feet.

5.4.5 Dermatology Life Quality Index (DLQI)

DLQI is a skin disease-specific Quality of Life (QoL) questionnaire comprised of 10 items assessing the subject's status over the previous week. DLQI can be used to assess 6 different aspects that may affect QoL: symptoms and feelings, daily activities, leisure, work, or school performance, personal relationships, and treatment. Each item is scored on a 4-point Likert scale: 0 = not at all/not relevant; 1 = a little; 2 = a lot; and 3 = very much. The item number 7 is a multi-part item, the first part of which ascertains whether the subject's skin prevented them from working or studying (Yes [3], No, or Not relevant [0]), and if "No," then the subject is asked how much of a problem the status has been at work or study over the past week, with response alternatives being "a lot (2)," "a little (1)," or "not at all (0)". The DLQI total score is derived by summing all item scores, which has a possible range of 0 to 30 with higher scores indicating increased disease severity and correspond to poorer quality of life.

DLQI total score is derived by summing all item scores, which has a possible range of 0 to 30, with 30 corresponding to the worst quality of life, and 0 corresponding to the best.

DLQI response (score of 0 or 1) is defined as subject's DLQI total score achieving 0 or 1.

CONFIDENTIAL

5.5 Analysis Phases

• Placebo-controlled Phase/Period – Weeks 0 to16

This period starts on the day of randomization (Week 0/Visit 2), and stops on below:

(1) the day of Week 16/Visit 8 if the subject continued study treatment to the active treatment phase

(2) the day of the discontinuation if the subject discontinued study treatment prior to or at Week 16/Visit 8

(3) the last known study day if the subject is lost to follow-up prior to or at Week 16/Visit 8

• Active Treatment Phase/Period – Weeks 16 to 52

This period starts on one day after the day of the dose of apremilast distributed at Week 16/Visit 8, and stops on either below.

(1) the day of Week 52/Visit 13

(2) the day of the discontinuation if the subject discontinued prior to or at Week 52/Visit13

(3) the last known study day if the subject lost to follow-up prior to or at Week 52/Visit 13 during the phase

For safety analysis, the period starts on the day of the first dose of apremilast in the period.

• Safety Follow-up Phase/Period

Subjects who complete or discontinue the study treatment, will be followed up for 30 days after the end of treatment visit.

For adverse event analysis, data from the first 30 days after the last dose of IP will be included in the precedent treatment phase and data after the 30 days will be presented separately.

• Apremilast exposure period

This period starts on the date of either:

- the first dose of IP following randomization (Week 0/Visit 2) for subject who are treated with apremilast from Week 0

- the first dose of IP from the IP dispensed at Week 16/Visit 8 for subjects who were originally treated with placebo and are switched to apremilast at Week 16

This period stops on either: (1) data restriction date; or (2) the end of the study.

During the apremilast-exposure period, data are presented by treatment sequence, i.e., Placebo/30 mg BID, 30 mg BID as Initiated, and a total column of 30 mg BID as Treated.

6. Populations for Analysis

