2.3 Benefit/Risk Assessment

Pivotal phase 3 studies demonstrated statistically significant and clinically meaningful improvement in the signs and symptoms of PsA, PsO, and BD in subjects given apremilast 30 mg BID. The most commonly observed treatment-emergent adverse

Protocol Number: 20200195

Date: 15 April 2022 Page 23 of 99

events (reported in ≥ 5% of subjects) included diarrhea, nausea, headache, upper respiratory tract infections, and nasopharyngitis, most of which occurred within the first 2 weeks of treatment and resolved within 4 weeks. Most treatment-emergent adverse events were mild or moderate in severity and resolved during continued apremilast treatment. The incidence of serious adverse events was low and comparable between apremilast and placebo treatment groups in placebo-controlled periods and was not driven by any single preferred term or specific individual organ toxicity. The safety profile of apremilast is comparable across its approved indications of PsA, PsO, and BD.

A phase 2 study (CC-10004-PPP-001 [20200055]) evaluated the risk and benefit of apremilast 30 mg BID in Japanese subjects with PPP. The results from this phase 2 study supported the efficacy of apremilast across multiple endpoints with safety and tolerability data consistent with the known safety profile of apremilast. Based on these results this phase 3 confirmatory trial is being implemented.

As of 20 March 2021, over 9000 subjects have received apremilast doses ranging from 10 to 105 mg/day in various completed and ongoing clinical studies and more than 736 035 unique patients worldwide have been treated with apremilast. Frequently reported adverse events have included gastrointestinal disorders (diarrhea, nausea, vomiting, abdominal discomfort) and nervous system disorders (headache). The benefit-risk balance of apremilast continues to remain favorable for approved indications.

Amgen closely monitors the COVID-19 pandemic around the world. As part of this effort, Amgen performs a rigorous assessment, considering the study design, patient safety, public health risk, benefit-risk assessment, as well as the burden on country healthcare systems. Decisions are made on a study-by-study and country-by-country basis to minimize risk to patients and avoid undue burden on healthcare facilities.

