8.1.2 Treatment Period

Visits will occur per the Schedule of Activities (Table 1-1). On-study visits may be completed as specified in the Schedule of Activities. The date of the first dose of apremilast is defined as day 1. All subsequent doses and study visits will be scheduled

Protocol Number: 20200195

Date: 15 April 2022 Page 44 of 99

based on the day 1 date. Apremilast is to be administered during each visit that it is required.

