The term disability means a substantial disruption of a person's ability to conduct normal life functions. This definition is not intended to include experiences of relatively minor medical significance such as uncomplicated headache, nausea, vomiting, diarrhea, influenza, and accidental trauma (eg, sprained ankle) which may interfere with or prevent everyday life functions but do not constitute a substantial disruption.

Is a congenital anomaly/birth defect

Other medically important serious event

Medical or scientific judgment is to be exercised in deciding whether serious adverse event reporting is appropriate in other situations such as important medical events that may not be immediately life-threatening or result in death or hospitalization but may jeopardize the subject or may require medical or surgical intervention to prevent 1 of

Protocol Number: 20200195

Date: 15 April 2022 Page 77 of 99

the other outcomes listed in the above definition. These events are typically to be considered serious.

Examples of such events include invasive or malignant cancers, intensive treatment in an emergency room or at home for allergic bronchospasm, blood dyscrasias or convulsions that do not result in hospitalization, or development of drug dependency or drug abuse.

Protocol Number: 20200195

Date: 15 April 2022 Page 78 of 99

Recording Adverse Events and Serious Adverse Events

Adverse Event and Serious Adverse Event Recording

- When an adverse event or serious adverse event occurs, it is the responsibility of the investigator to review all documentation (eg, hospital progress notes, laboratory, and diagnostics reports) related to the event.
- The investigator will then record all relevant adverse event/serious adverse event information in the Event Case Report Form (CRF).
- The investigator must assign the following mandatory adverse event attributes:
 - Adverse event diagnosis or syndrome(s), if known (if not known, signs or symptoms);
 - Dates of onset and resolution (if resolved);
 - Did the event start prior to first dose of investigational product
 - Assessment of seriousness;
 - Severity (or toxicity defined below);
 - Assessment of relatedness to apremilast, other protocol-required therapies and/or study-mandated activity and/or procedures;
 - Action taken; and
 - Outcome of event.

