Week 24 (Visit 10)	169	One day after the first apremilast dosing day on Visit 8 – 197			
Week 32 (Visit 11)	225	Study Day 198 – 225			
Week 52 (Visit 13)	365	Study Day 226 – End of the Period			

Active treatment period start point for adverse event data shall be the first apremilast dosing day on Visit 8.

Appendix C. Handling of Dates, Incomplete Dates and Missing Dates Imputation Rules for Partial or Missing Start Dates

		Stop Date						
		Complete: yyyymmdd		Partial: yyyymm		Partial: УУУУ		Missing
Start Date		< 1 st dose	≥ 1 st dose	< 1 st dose	≥ 1 st dose	< 1 st dose	≥ 1 st dose	
				уууутт	уууутт	уууу	уууу	
Partial:	= 1 st dose yyyymm	2	1	n/a	1	n/a	1	1
уууутт	≠ 1 st dose		2	2	2	2	2	2
	уууутт					,		
Partial:	= 1 st dose		1		1	n/a	1	1
уууу	уууу	3		3				
	≠ 1 st dose		3		3	3	3	3
	уууу							
Mis	sing	4	1	4	1	4	1	1

The reference date for the following rules is the date of first dose of apremilast.

1=Impute the date of first dose; 2=Impute the first of the month; 3=Impute January 1 of the year; 4=Impute January 1 of the stop year

Note: For subjects who were never treated (first dose date is missing), partial start dates will be set to the first day of the partial month or first day of year if month is also missing.

Imputation Rules for Partial or Missing Stop Dates

Initial imputation

- If the month and year are present, impute the last day of that month.
- If only the year is present, impute December 31 of that year.
- If the stop date is entirely missing, assume the event or medication is ongoing.

If the imputed stop date is before the start date, set stop date to missing.

If the imputed stop date is after the death date, impute as death date.

Imputation Rules for Partial or Missing Death Dates

If death year and month are available but day is missing:

- If yyyymm for the date last known to be alive equals yyyymm for death date, set death date to the day after the date last known to be alive.
- If yyyymm for the date last known to be alive is less than the yyyymm for death date, set death date to the first day of the death month.
- If yyyymm for the date last known to be alive is greater than yyyymm for death date, assume date last known to be alive is in error, set death date to the first day of the death month.

If month and day are missing and year of death is known:

- If yyyy for the date last known to be alive equals yyyy for death date, set death date to the day after last known to be alive date.

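### For adverse events, the SAP's period boundaries leave a placebo switcher's first apremilast day in the placebo-controlled period as well as in the apremilast periods

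*SAP*

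**What the plan says.** SAP 5.5 defines the analysis phases by calendar day.

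- **End of the placebo-controlled period**, for subjects who go on to active treatment: "the day of Week 16/Visit 8 if the subject continued study treatment to the active treatment phase". No separate end is given for safety or adverse event data.
- **Start of the active treatment period, general rule:** "This period starts on one day after the day of the dose of apremilast distributed at Week 16/Visit 8".
- **Start of the active treatment period, safety:** "For safety analysis, the period starts on the day of the first dose of apremilast in the period". Appendix B repeats this below its visit-window tables: "Active treatment period start point for adverse event data shall be the first apremilast dosing day on Visit 8".
- **Start of the apremilast-exposure period for switchers:** "the first dose of IP from the IP dispensed at Week 16/Visit 8 for subjects who were originally treated with placebo".

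On when that first dose is taken, Protocol 8.1.2 says: "Apremilast is to be administered during each visit that it is required". The Schedule of Activities has product dispensed at Visit 8.

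**The concern.** Under the general rule the two periods meet without overlapping if the first dose is taken at the visit: the Visit 8 day belongs to the placebo-controlled period and the active period begins the next day. The safety rule moves the active start back to the dosing day, but nothing moves the placebo-controlled end back with it. The dosing day then sits in both periods.

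For a subject randomized to placebo, that day is the first day on apremilast. An event that begins after the dose is an on-apremilast event, yet on the written boundaries it also belongs to the placebo-controlled period, where results are shown by treatment group (SAP 9.6). It would appear under placebo.

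The placebo-controlled adverse event table is the only randomized safety comparison and serves the secondary objective on safety and tolerability. Protocol 2.3 says of the commonest events, which include diarrhea and nausea, that they were ones "most of which occurred within the first 2 weeks of treatment and resolved within 4 weeks". The day at issue is therefore the start of the period when such events are expected. SAP 7.3 and 7.4 state that the placebo-controlled analyses will not be repeated at the supplemental or final analysis, so a later data cut would not correct the table.

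**Working it through.** **Step 1. Reproduce the plan's figure.** Appendix B sets the target day as visit week × 7 + 1. For Week 16, 16 × 7 + 1 = 113, which matches the tabulated Visit 8 target day.

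**Step 2. Lay out the periods as study days**, for a switcher whose Visit 8 and first apremilast dose both fall on Day 113.

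| Rule | Placebo-controlled | Active treatment | Days in both |
|---|---|---|---|
| General | 1 to 113 | from 114 | 0 |
| Safety and adverse events | 1 to 113 | from 113 | 1 (Day 113) |
| Adverse events, with the proposed change | 1 to 112 | from 113 | 0 |

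The apremilast-exposure period for this subject also starts on Day 113.

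**Step 3. Look for a rule that would settle a Day 113 event.**

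- *Onset time.* The mandatory event attributes in Protocol Appendix 4 (Section 11.4) ask for onset and resolution dates. No clock time is listed. The pre-dose question there refers to the first dose of investigational product, which for a switcher was placebo at Week 0.
- *As-treated rule.* SAP 6.2 moves subjects with at least one apremilast dose in the placebo-controlled period to the apremilast group, but only where the wrong product was received inadvertently. It does not address the planned switch.
- *Treatment-emergent definition.* SAP 5.1.1 counts from the first dose of any investigational product, so the event qualifies and is not filtered out.

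None of these resolves the day.

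**Step 4. Direction.** In the placebo-controlled comparison, subjects already on apremilast have no first-day effect at Visit 8. Misattributed events can enter only the placebo column.

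**Step 5. Illustrative size.** Inputs: 85 subjects per group and 5% dropout before Week 16 (SAP 3.2). Switchers: 85 × 0.95 = 80.75, about 81. The documents give no rate of new events on the first apremilast day, so the rate *r* is assumed.

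- Extra placebo subjects, at most: 80.75 × *r*
- Percentage points on 85, at most: 100 × 80.75 × *r* / 85 = 95 × *r*

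| Assumed *r* | Extra placebo subjects | Percentage points |
|---|---|---|
| 1% | 0.8 | 0.95 |
| 2% | 1.6 | 1.9 |
| 5% | 4.0 | 4.75 |

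For each assumed rate these are ceilings. The tables count subjects, so someone who already had the same event in the placebo-controlled period adds nothing to that row. Someone with any earlier treatment-emergent event adds nothing to the overall row.

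**The case against.** The strongest reply is that the adverse event rules in SAP 5.5 and Appendix B are the specific ones and set the cut point for both periods. The phases are labelled consecutively, Weeks 0 to 16 and Weeks 16 to 52, and the authors plainly had the dosing day in mind when they assigned it to apremilast. On that reading an event on that day moves to the active period and is not duplicated. A reader might infer from the overlap that the SAP prescribes double counting. It does not say so. The double assignment follows from inclusive boundaries without a tie-break, and table or programming specifications outside these documents may already resolve it. The reply still relies on an implied end date that contradicts the stated one.

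A second reply is that appearing in two tables is no fault in itself. That is right: for subjects who start on apremilast, events before Week 16 belong in both the placebo-controlled and the apremilast-exposure tables by design. The fault is confined to the placebo-column attribution for switchers.

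Third, the upper end of the range may be too high. Protocol 2.3 speaks of the first 2 weeks and says nothing about the first day. Table 6-1 lists a single 10 mg dose on Day 1 of a titration meant to limit gastrointestinal effects. This stands, and the lower end may be more realistic.

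Fourth, SAP 9.6.2 tabulates onset by exposure interval with a separate category beyond 16 weeks. On an inclusive count Day 113 is 113/7 = 16.1 weeks, so such events could be visible there. They would, however, be shown as late placebo events, and the overall incidence tables would give no such signal.

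Finally, the overlap also lets a pre-dose event on the Visit 8 day enter the apremilast-exposure summaries. That is true, but it does not affect the randomized comparison.

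**Conclusion.** The point holds as a boundary error in the text. For adverse events the active-period start was moved to the dosing day and the placebo-controlled end was left where it was. Read literally, a switcher's first apremilast day counts toward placebo in the randomized safety table, and there the error can only raise placebo incidence and so flatter apremilast.

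The size is modest. It is one calendar day, in descriptive tables for which SAP 9.6.1 plans no inferential testing. If 1% to 5% of about 81 switchers had a new event starting that day, placebo would gain at most about 1 to 4 subjects, or about 1 to 5 percentage points on 85. This rests on the assumed first-day rate, on the planned group size and dropout, and on the first dose being taken on the Visit 8 day. If that dose is taken on a later day, there is no overlap.

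Two stronger conclusions are not supported. The range is not an estimate of bias in this trial, because the documents contain no first-day rate. Nor does the overlap reach efficacy: the general rule keeps those periods apart, and the primary test and sample size do not depend on it.

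**What to change.** Add one sentence to SAP 5.5. For adverse event analysis in subjects who continue into the active treatment phase, the placebo-controlled period ends on the day before the first apremilast dose from the product dispensed at Visit 8, and events starting on that dosing day belong only to the active treatment and apremilast-exposure periods. Repeat or cross-refer to it at the Appendix B note on adverse event data.

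Tying the end to the dose date, and not to the visit date, also covers a first dose taken after the visit day. The rule applies to both randomized groups, so follow-up in the placebo-controlled table stays comparable.

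The cost is that sentence and one date condition in the programs, with no new data and no change to trial conduct. The downside is small: for placebo switchers, an event that began before the dose on that day is attributed to apremilast. That is the conservative direction, and it is unavoidable without onset times.
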